## 5.2.3. Placement of the LIFESTREAM™ Covered Stent

The use of up to two (2) LIFESTREAM™ Covered Stents (placed in an overlapping fashion) is acceptable in this study (per side in bilateral disease). The recommended overlap distance between the two (2) LIFESTREAM™ Covered Stents is approximately 10 mm.

In the case of a geographic miss (or dissection) which necessitates placement of more than two (2) LIFESTREAM™ Covered Stents, one more LIFESTREAM™ Covered Stent may be placed (three total subject devices). However, if a dissection extends down to or includes the internal iliac artery, standard of care should be applied, including the placement of a commercially-available stent, which does not include the LIFESTREAM™ Covered Stent (unless the internal iliac was already occluded). In this case, the subject will be included in the ITT analysis.

Kissing stents may be placed at CIA ostial lesions. In the case of unilateral ostial disease, a LIFESTREAM™ Covered Stent may be placed in the healthy contralateral vessel (i.e., bilateral treatment using kissing stents), as this is standard of care when placing covered stents. In such a case, the healthy vessel would also become a treatment vessel (i.e., unilateral disease, but bilateral treatment due to ostial disease). No crossover procedures are allowed for treatment of outflow disease once kissing stents are placed.

**It is required that a pre-deployment angiographic image(s) of the LIFESTREAM™ Covered Stent(s) be captured.**

**It is required that angiographic image(s) of the fully-inflated LIFESTREAM™ Covered Stent balloon(s) be captured.**

**It is required that a post-deployment angiographic image(s) of the LIFESTREAM™ Covered Stent(s) be captured.**

Post-dilatation of each LIFESTREAM™ Covered Stent can be performed to ensure proper expansion of the LIFESTREAM™ Covered Stent. If post-dilated, the Investigator should select a balloon size of the same approximate diameter as the native vessel. **Balloon dilation of the healthy vessel beyond the proximal or distal edges of the LIFESTREAM™ Covered Stent should be avoided.**

**If post-dilated, it is required that the post-dilatation angiographic image(s) of the LIFESTREAM™ Covered Stent be captured.**

All angiography shall be performed using the identical angles, magnification and angiographic technique as described in the “Angiography Guidelines” supplied by the Angiographic Core Lab.

#### **5.2.4. Intra-Procedure – Other Treatment Modalities**

If the entirety of the lesion(s) cannot be treated to an angiographically acceptable result, consideration should be given to other medically-appropriate treatment modalities, in each case, as dictated by clinical circumstances, institutional standard of care, and Investigator preference. All subjects that receive a LIFESTREAM™ Covered Stent and undergo other treatment modalities will be followed per protocol specifications, will be documented, and included in the ITT analysis. If a subject is converted to bypass surgery and the LIFESTREAM™ Covered Stent is explanted, then the subject will be followed through the 30-day follow-up visit to assess any safety events and will also be included in the ITT. An emergent intervention of any kind is allowed at any time at the discretion of the Investigator, and should be documented in the medical record/source documents.

### 5.2.5. Final Angiogram

Completion angiography of the distal infrapopliteal vessels should be performed to rule-out the possibility of distal embolization. **Properly-labeled angiographic-recorded media are to be uploaded or sent to the Angiographic Core Lab for evaluation.**

### 5.2.6. Guide Catheter/Sheath Removal Guidelines

Immediately following the procedure, in accordance with the institution's standard of care practices, heparin should be discontinued. An on-label vascular closure device may be used at the discretion of the Investigator, in accordance with the manufacturer's directions. The index procedure ends at the time that the last guidewire is removed.

### 5.2.7. Post-Procedure Medications

Treated subjects are to receive a minimum of 75 mg of ASA orally per day for a minimum of 6 months, and a minimum of 75 mg of clopidogrel orally per day for a minimum of 3 months. Subjects should be excluded if they have an allergy to aspirin at baseline. Ticlopidine may be prescribed if the subject has an allergy or contraindication to Clopidogrel. Clopidogrel is not required if a subject is taking warfarin, prasugrel, ticagrelor, and/or approved direct thrombin inhibitors (e.g., dabigatran) or factor Xa inhibitors (e.g., rivaroxaban, apixaban); however the subject should receive a minimum of 75 mg of ASA orally per day for a minimum of 6 months. Investigators may elect to use additional anticoagulants, for example, low molecular weight heparin as they deem medically appropriate. If the treated subject requires subsequent surgery that necessitates the discontinuation of these medications, then the subject is to resume protocol required medications as soon as possible after the medical procedure.

## 5.3. Hospital Discharge Procedures

Prior to hospital discharge, each treated subject should have the following examinations/assessments performed:

- Comprehensive physical examination of the subject's overall health status, including:
  - Target Limb Assessment
  - Concomitant Medication(s): antiplatelets, anticoagulants, direct thrombin inhibitors, and factor Xa inhibitors (e.g., ASA, clopidogrel, ticlopidine, prasugrel, ticagrelor, warfarin, dabigatran, rivaroxaban, apixaban)
- Documentation of occurrence of Adverse Events (AEs) or serious adverse events (SAEs) since index procedure.

## 5.4. Subject Follow-Up

All treated subjects who receive a LIFESTREAM™ Covered Stent will be followed at 30-days and 6-, 9-, 12-, 24-, and 36-months post-index procedure.

---

#### 5.4.1. 30-Day Follow-Up Visit (30 Days ± 7 Days)

- Comprehensive physical examination of the subject’s overall health status, including:
  - Target Limb Assessment
  - Concomitant Medication(s): antiplatelets, anticoagulants, direct thrombin inhibitors, and factor Xa inhibitors (e.g., ASA, clopidogrel, ticlopidine, prasugrel, ticagrelor, warfarin, dabigatran, rivaroxaban, apixaban)
- Comprehensive physical examination of the subject’s vascular status, including:
  - Resting bilateral ABIs
  - DUS of Target Limb employing “Ultrasound Guidelines”
    - DUS images shall be uploaded or sent to the Ultrasound Core Laboratory for evaluation.
  - Rutherford Category & Grade Assignment
- Documentation of occurrence of AEs or SAEs since discharge.
- Documentation of occurrence of TLR/TVR since discharge. If TLR/TVR was performed, properly labeled angiographic-recorded media shall be uploaded or sent to the Angiographic Core Laboratory for evaluation.
- Quality of Life Assessment (WIQ)

#### 5.4.2. 6-Month Telephone Screening (180 Days ± 30 Days)

- Documentation of Concomitant Medication(s): antiplatelets, anticoagulants, direct thrombin inhibitors, and factor Xa inhibitors (e.g., ASA, clopidogrel, ticlopidine, prasugrel, ticagrelor, warfarin, dabigatran, rivaroxaban, apixaban)
- Documentation of occurrence of AEs or SAEs since last visit.
- Documentation of occurrence of TLR/TVR since last visit. If TLR/TVR was performed, properly labeled angiographic-recorded media shall be uploaded or sent to the Angiographic Core Laboratory for evaluation.

Note, this information may also be collected at an office visit (instead of a telephone screen), as long as the visit occurs within the above mentioned follow-up window.

#### 5.4.3. 9-Month Follow-Up Visit (270 Days ± 30 Days)

- Comprehensive physical examination of the subject’s overall health status, including:
  - Target Limb Assessment
  - Concomitant Medication(s): antiplatelets, anticoagulants, direct thrombin inhibitors, and factor Xa inhibitors (e.g., ASA, clopidogrel, ticlopidine, prasugrel, ticagrelor, warfarin, dabigatran, rivaroxaban, apixaban)
- Comprehensive physical examination of the subject’s vascular status, including:
  - Resting bilateral ABIs
  - DUS of Target Limb employing “Ultrasound Guidelines”
    - DUS images shall be uploaded or sent to the Ultrasound Core Laboratory for evaluation.
  - Rutherford Category & Grade Assignment
- Documentation of occurrence of AEs or SAEs since last visit.

- Documentation of occurrence of TLR/TVR since last visit. If TLR/TVR was performed, properly labeled angiographic-recorded media shall be uploaded or sent to the Angiographic Core Laboratory for evaluation.
- Quality of Life Assessment (WIQ)

#### **5.4.4. 12-Month (1 Year) Follow-Up Visit (365 Days ± 30 Days)**

- Comprehensive physical examination of the subject’s overall health status, including:
  - Target Limb Assessment
  - Concomitant Medication(s): antiplatelets, anticoagulants, direct thrombin inhibitors, and factor Xa inhibitors (e.g., ASA, clopidogrel, ticlopidine, prasugrel, ticagrelor, warfarin, dabigatran, rivaroxaban, apixaban)
- Comprehensive physical examination of the subject’s vascular status, including:
  - Resting bilateral ABIs
  - DUS of Target Limb employing “Ultrasound Guidelines”
    - DUS images shall be uploaded or sent to the Ultrasound Core Laboratory for evaluation.
  - Rutherford Category & Grade Assignment
- Documentation of occurrence of AEs or SAEs since last visit.
- Documentation of occurrence of TLR/TVR since last visit. If TLR/TVR was performed, properly-labeled, angiographic-recorded media shall be uploaded or sent to the Angiographic Core Laboratory for evaluation.
- Quality of Life Assessment (WIQ)

#### **5.4.5. 24-Month (2 Year) Follow-Up Visit (730 Days ± 30 Days)**

- Comprehensive physical examination of the subject’s overall health status, including:
  - Target Limb Assessment
  - Concomitant Medication(s): antiplatelets, anticoagulants, direct thrombin inhibitors, and factor Xa inhibitors (e.g., ASA, clopidogrel, ticlopidine, prasugrel, ticagrelor, warfarin, dabigatran, rivaroxaban, apixaban)
- Comprehensive physical examination of the subject’s vascular status, including:
  - Resting bilateral ABIs
  - DUS of Target Limb employing “Ultrasound Guidelines”
    - DUS images shall be uploaded or sent to the Ultrasound Core Laboratory for evaluation.
  - Rutherford Category & Grade Assignment
- Documentation of occurrence of AEs or SAEs since last visit.
- Documentation of occurrence of TLR/TVR since last visit. If TLR/TVR was performed, properly-labeled, angiographic-recorded media shall be uploaded or sent to the Angiographic Core Laboratory for evaluation.
- Quality of Life Assessment (WIQ)

#### **5.4.6. 36-Month (3 Year) Follow-Up Visit (1095 Days ± 30 Days)**

- Comprehensive physical examination of the subject’s overall health status, including:

- Target Limb Assessment
- Concomitant Medication(s): antiplatelets, anticoagulants, direct thrombin inhibitors, and factor Xa inhibitors (e.g., ASA, clopidogrel, ticlopidine, prasugrel, ticagrelor, warfarin, dabigatran, rivaroxaban, apixaban)
- Comprehensive physical examination of the subject’s vascular status, including:
  - Resting bilateral ABIs
  - DUS of Target Limb employing “Ultrasound Guidelines”
    - DUS images shall be uploaded or sent to the Ultrasound Core Laboratory for evaluation.
  - Rutherford Category & Grade Assignment
- Documentation of occurrence of AEs or SAEs since last visit.
- Documentation of occurrence of TLR/TVR since last visit. If TLR/TVR was performed, properly-labeled, angiographic-recorded media shall be uploaded or sent to the Angiographic Core Laboratory for evaluation.
- Quality of Life Assessment (WIQ)

## 5.5. Subject Discontinuation

The follow-up period for this study is 36 months (1095 Days  $\pm$  30 Days). Subjects may be discontinued for the following reasons:

- Lost to Follow-Up (LTF): A subject may be considered LTF if the site personnel are unable to locate the subject despite two documented attempts to notify the subject via telephone and a third attempt by certified mail. Before the site considers a subject LTF, written agreement should be obtained from Bard.
- Withdrawn Consent: The subject requests to terminate his/her participation in the study (the Investigator, or authorized designee, must attempt to identify and document the reasons for termination).
- Death: The subject becomes deceased. If known, the cause of death should be documented.
- Withdrawal by Investigator: Participation may be immediately terminated by the Investigator if, in the opinion of the Investigator, the subject would be exposed to inappropriate risk by continuing in the study. Additionally, the Investigator may terminate a subject’s participation with prior written approval from Bard if the subject is repeatedly noncompliant with study procedures.
- Study Termination: The study is terminated by Bard. (See Section 16)

Additional subjects will not be enrolled to replace those who withdraw from the study.

---

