### Treated Subject

After the subject has met all eligibility criteria, undergone successful PTA of the target lesion(s), and the LIFESTREAM™ Covered Stent catheter is introduced (i.e., delivery system enters the subject's body), the subject will be considered to be a treated subject in the study. Treated subjects will continue study participation through the study's 36-month follow-up period. Subjects that do not receive the LIFESTREAM™ Covered Stent implant (but the LIFESTREAM™ Covered Stent catheter was introduced) will be followed through the 30-day follow-up visit to assess any safety events and will be included in the ITT and PP analyses (see Section 6).

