## 6. STATISTICAL ANALYSIS PLAN

### 6.1. Analysis Populations

The ITT population consists of those subjects who have signed the Informed Consent Form and had the LIFESTREAM™ Covered Stent catheter introduced (i.e., delivery system enters the subject's body).

Subjects who do not receive the study implant (section 5.2.2), but the LIFESTREAM™ Covered Stent catheter was introduced will be included in the ITT population. Subjects who need more than two (2) LIFESTREAM™ Covered Stents (section 5.2.3) or undergo other treatment modalities (section 5.2.4) will be included in the ITT population.

A per-protocol (PP) population may be created if there are subjects who have any major protocol deviations. Major Protocol Deviations are defined as those that occur to protect the life or physical well-being of a subject in an emergency, or those that may affect the scientific soundness of the study, or the rights, safety or welfare of human subjects. The PP population will consist of any subjects in the ITT population who do not have any major protocol deviations, including deviations of study eligibility criteria. Subjects who do not receive the study implant (section 5.2.2), but the LIFESTREAM™ Covered Stent catheter was introduced will be included in the PP population. Subjects who need more than two (2) LIFESTREAM™ Covered Stents and require placement of a commercially-available stent (section 5.2.3), or undergo other treatment modalities (section 5.2.4) will be excluded from the PP population.

All effectiveness and safety analyses including the primary analysis will be primarily based on the ITT population. A PP analysis may also be performed for the primary endpoint. It will only serve as a sensitivity analysis for the primary analysis which is based on the ITT population.

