## 6.6. Handling of Missing Data

Study endpoints may be missing due to withdrawal of consent, investigator's decision, lost to follow-up and death. As long as the missing data is unrelated to the study intervention and the observed and unobserved data, limiting the analysis to those subjects who contribute endpoints produces unbiased estimates of the event rates.

Additionally, Kaplan-Meier survival analyses will be performed to estimate the event rates at various time-points. In survival analyses, unobserved endpoints are a standard part of the analysis. They are known as censored observations.

The reason for missing data for all subjects will be reported. If there is any indication that missing data is related to the study intervention, a worst-case analysis may be performed in addition to the standard analysis. In a worst-case analysis, a failure of effectiveness or safety will be assumed to have occurred at the time the subject was censored.

In addition, regardless of whether missing data are related to the study intervention, a tipping-point analysis will be performed, in which assumptions about missing data are varied from worst-case to best-case to examine at what point the missing data would alter the results of the analysis.

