## 16. TERMINATION OF STUDY

Bard reserves the right to suspend enrollment or terminate the study at any time as set forth in the CSA. Written notice will be submitted to the Investigator in advance of such termination. Bard may suspend enrollment or terminate the study at a specific site for reasons including, but not limited to, inadequate data collection, low subject enrollment rate, achievement of the total enrollment, or non-compliance with this protocol or other clinical research requirements. In the event of study termination, treated subjects must be followed through the 3-year study follow-up period.

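### Section 5.5 lets an investigator, with sponsor approval, end follow-up of an implanted subject for undefined noncompliance, with no endpoint collection afterwards; a failure not yet detected can then fall outside the primary test

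*Combined protocol and SAP*

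**What the plan says.** **Intended follow-up.** Section 5.2.2, on treated subjects, says "Treated subjects will continue study participation through the" 36-month follow-up period. Subjects in whom the catheter was introduced but no stent implanted are followed to 30 days only, so this point concerns implanted subjects.

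**Discontinuation.** Section 5.5 has two routes for withdrawal by the investigator. One is immediate, on grounds of inappropriate risk. The other ends "participation with prior written approval from Bard if the subject is repeatedly noncompliant with study procedures". It gives no number of missed visits or procedures and no list of data still to be collected. It adds: "Additional subjects will not be enrolled to replace those who withdraw from the study".

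**Analysis.** Section 6.1 states: "All effectiveness and safety analyses including the primary analysis will be primarily based on the ITT population". Section 6.6 then lists the ways an endpoint can be missing: withdrawn consent, the investigator's "decision, lost to follow-up and death". Provided missingness is unrelated to the intervention and to the data, observed or not, it holds that "limiting the analysis to those subjects who contribute endpoints produces unbiased estimates of the event rates". Section 6.8 bases the tests on 93 evaluable of 103 and 139 evaluable of 154.

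**Safeguards in Section 6.6.** Reasons for missing data are reported for every subject. A tipping-point analysis is mandatory. A worst-case analysis is optional, if missingness looks related to the intervention. Section 6.2 makes success depend only on the one-sided exact binomial p-value (below 0.0335 at interim, 0.0325 at final).

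**The concern.** Once a stent is implanted, ending participation cannot change exposure; it only stops the collection of outcomes. The decision is taken by an investigator who knows the subject's course in an open-label, single-arm study, and it is approved by the sponsor without stated criteria. By month 9 the investigator has the 30-day ABI, Rutherford category and duplex visit (Section 5.4.1) and the 6-month report of adverse events and revascularisations (Section 5.4.2).

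Noncompliance may be related to outcome, so missingness created this way is hard to square with the condition in Section 6.6. The events exposed are those not yet detected: a later TLR or amputation, or restenosis that only the 9-month scan would show. If they go unobserved, the observed event rate is too low and the test against 19.5% is too lenient. The ITT label does not prevent this, because no section assigns a primary outcome to an ITT subject without an endpoint.

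**Working it through.** **Inputs.** Performance goal 19.5%, assumed rate 10.5%, 139 evaluable and 154 treated (Section 6.7); interim and final evaluable numbers 93 and 139, overall one-sided error 0.05 (Section 6.8); p-value limits 0.0335 and 0.0325 (Section 6.2). The documents give no share of failures lost through discontinuation, so every share below is an assumption.

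**1. Reproduce the plan.** The p-value is P(X ≤ x), with X ~ Binomial(n, 0.195).
- n = 139 at 0.05: reject at ≤ 19 events; size 0.0474; power at 10.5% is 90.9% (Table 2, without interim: 91.1%).
- Interim: 10/93 gives 0.0178 (pass) and 11/93 gives 0.0356 (fail), so the cut-off is ≤ 10.
- Final: 18/139 gives 0.0284 (pass) and 19/139 gives 0.0474 (fail), so the cut-off is ≤ 18.
- Two-look success = P(X₉₃ ≤ 10) + Σ P(X₉₃ = x)·P(X₄₆ ≤ 18 − x), summed over x = 11 to 18. At 10.5%: interim 61.4%, overall 86.9% (Table 2: 61.3%, 87.1%). At 19.5%: 1.8% and 3.65% (Table 2: 1.8%, 3.8%).

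The plan's figures are reproduced to within simulation error.

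**2. One would-be event lost at the boundary.**
- Final: 19/139, p = 0.0474, fails; 18/138, p = 0.0310, succeeds.
- Interim: 11/93, p = 0.0356, fails; 10/92, p = 0.0199, succeeds.

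**3. Selective loss under a true rate of 19.5%.** Suppose a share q of would-be events, and no non-events, is lost. The rate among those analysed is 0.195(1 − q)/(1 − 0.195q). The evaluable numbers stay at 93 and 139. Among 154 treated subjects, 154 × 0.195 = 30.0 would-be events are expected.

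| q (assumed) | would-be events lost, of 30.0 | rate analysed | two-look false success |
|---|---|---|---|
| 0 | 0 | 19.5% | 3.65% |
| 5% | 1.5 | 18.7% | 5.8% |
| 10% | 3.0 | 17.9% | 8.9% |

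**4. Dependence on the model.** Simulation on 103 and 154 treated subjects, with no other dropout, gives 3.7%, 6.4% and 10.1% for the same three shares. With total missingness held at the planned 10%, it gives 3.9% if failures and non-failures are lost equally, and 7.0% if 15% of failures and 8.8% of non-failures are missing. What matters is the difference in loss between failures and non-failures: equal loss does no harm, and a net excess of one to two failures takes the error past 5%.

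**The case against.** **What stands.**
- Section 6.2 contains no rule for dropping subjects. The exclusion is inferred from Section 6.6 and the evaluable counts in Section 6.8, and Section 6.6 is conditional on missingness being unrelated to the data.
- Only a 30-day visit and a 6-month call fall between discharge and the 9-month visit, which leaves little time to become repeatedly noncompliant. A subject who skips the 9-month scan lacks a restenosis reading whether or not formally terminated. The clause's own contribution may be small, and terminations after 9 months cannot affect the primary test.
- The shares are assumed, and step 3 removes failures only. The one-event example partly reflects the discreteness of an exact test at its boundary.
- Prior written approval documents each decision and limits the investigator's discretion. Reported reasons, the tipping-point analysis, the independent core laboratories and the events committee are real safeguards. None of them restores an endpoint that was never collected, and none alters the success rule.

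**Stronger readings the documents do not support.**
- A reader might infer that a recorded TLR, amputation, MI or restenosis disappears when the subject is terminated. Nothing says so; a recorded event is a contributed endpoint.
- A reader might infer that subjects were, or were meant to be, removed to improve the result. Nothing shows this.
- A reader might set "Study Termination: The study is terminated by Bard" in Section 5.5 against "In the event of study termination, treated subjects must be followed through the 3-year study follow-up period" in Section 16 and see a contradiction. The Section 5.5 bullet itself refers the reader to Section 16, so the two are already connected and the matter is at most editorial.

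**Conclusion.** The weakness is real but limited. Section 5.5 permits a discretionary, loosely defined end to outcome collection in subjects who carry a permanent implant. Sections 6.6 and 6.8, read together, let a resulting undetected failure fall outside the primary test, and the sensitivity analyses do not feed into Section 6.2.

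The size is illustrative. One lost would-be event can reverse a result at the boundary. A 5% failures-only loss, about 1.5 subjects of 154, raises the false-success rate at 19.5% from 3.65% to about 5.8%, or 6.4% under the alternative setup, against the 5% limit. These figures assume that would-be failures are lost preferentially and that the primary test uses evaluable subjects only. They show how sensitive the test is; they do not forecast how often the clause would be used. The change is worth making because it removes an avoidable source of missing data at little cost.

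**What to change.** **Section 5.5.** Delete the sentence allowing termination for noncompliance. State that, unless consent is withdrawn, a treated subject due for 36-month follow-up who misses visits or procedures, or is withdrawn by the investigator for any reason, stays in follow-up for data collection. TLR, major amputation, MI and vital status are then obtained by telephone or from records, and the 9-month duplex scan is still sought and used if obtained.

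**Section 6.6.** State that a subject without a duplex scan may not be counted as restenosis-free on telephone contact alone. Such subjects remain missing for restenosis and enter the tipping-point analysis, with those whose missingness follows an investigator or sponsor decision reported separately.

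**Cost and limits.** Protocol wording and a few extra telephone or record checks; no added subjects or procedures, and no change to the hypothesis, thresholds or sample size. The gap closes only in part: telephone and records cannot detect restenosis, so it stays unobserved in subjects who never have the scan.
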